16.3 Analysis Plan

The analysis for this trial will commence at planned time points (see 16.2) and at the time the patients have become evaluable for the primary endpoint. The Statistician and Study Chair will make the decision, in accord with CCS Standard Operating Procedures, availability of data for secondary endpoints (e.g., laboratory correlates), and the level of

data maturity. It is anticipated that the earliest date in which the results will be made available via manuscript, abstract, or presentation format is when last patient has been followed for at least 6 months.

16.31 Primary Outcome Analysis

- 16.311 Definition: The primary endpoint of this trial is the complete response rate at the end of induction as determined by investigator on the basis of PET-CT scans according to Lugano 2014. A complete response is defined as an objective status of CR at the end of induction. All patients meeting the eligibility criteria who have signed a consent form and have begun treatment will be evaluable for response, unless they are determined to be a major violation. Only MCL patients treated at the final dose level will be included when evaluating the decision rules in Sections 16.211 and 16.212. Patients without MCL and patients treated at other dose levels will be summarized separately.
- 16.312 Estimation: The proportion of success will be estimated by the number of success divided by the total number of evaluable patients. 95% confidence intervals for the true success proportion will be calculated according to the approach of Duffy and Santner³.
- 16.313 Over Accrual: If more than the target number of patients are accrued, the additional patients will not be used to evaluate the stopping rule or used in any decision-making process; however, they will be included in final point estimates and confidence intervals.

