22 ACCRU LY-1806

4.0 Test Schedule

	Days Prior to Registration			Induction (21-day cycles)			EOI ¹	Maintenance (12 months)	EOM ²	Post- Treatment	
Tests and Procedures	≤ 30	≤ 14		ycle ±1 d		Cycle 2 (±2 d)	Cycles 3-6 (±2 d)	After last induction	Monthly (30days)	35 days after last dose	clinical follow- up period (q3m for 2 years
	days	days	D1	D8	D15	D1	D1	dose	(±1 week) D1	(±14 days)	+/- 14 days)
Complete Medical history	X										
ECOG Performance Status	X		X	X	X	X	X	X	X	X	X
Physical exam, weight and vital signs (blood pressure, pulse, O2) ⁴	X		X	X	X	X	X	X	X	X	X
Height	X										
12-lead EKG ⁸	X										
MUGA/echocardiogram ⁸	X										
Hematology (CBC and diff)		X	X16	X	X	weekly ¹⁸	X	X	X	X	
Chemistry Labs ⁷		X	X 16	X	X	X	X	X	X	X	
Coagulation (INR, aPTT [or PTT], and PT)		X									
Serum Pregnancy test ³		X^3	X^3			X^3	X ³	X	X^3	X^3	
HIV ¹⁴ , HBV ¹³ , HCV ⁶	X										
Quantitative IgA, IgG, IgM			X					X		X	X
Optional Whole blood for MRD ¹⁷			X					X		X	
Optional Immunology Research Blood ^{12 R}			X ¹²				X ¹²	X^{12}	X ¹²		X ¹²

	Days Prior to Registration			Induction (21-day cycles) EOI ¹		Maintenance (12 months)	EOM ²	Post- Treatment clinical follow-			
Tests and Procedures	≤ 30	≤ 14	l	Cycle 1 (±1 d)		Cycle 2 (±2 d)	Cycles 3-6 (±2 d)	After last induction	(Soddys)	35 days after last dose	
	days	days	D1	D8	D15	D1	D1	dose	(±1 week) D1	(±14 days)	+/- 14 days)
Review Patient Medication Diary ¹⁵				X	X	X	X	X	X		
Optional tissue specimen R			X ¹¹					X^{11}			
Mandatory tissue specimen 19 R	X										
Concomitant medications	X					To be	recorded conti	inually until er	nd of treatment		
Adverse Event Assessment ⁵	X					To be assessed	d continually				
PET-CT scan	X							X	X ⁹	X	X ⁹
Bone marrow biopsy and aspirate	X^{10}							X^{10}			

¹ End of induction (EOI) is between 28-42 days after the last induction dose of rituximab and hyaluronidase human and polatuzumab vedotin.

² End of maintenance (EOM) visit may take place at 35 days +/- 14 days from the last dose of venetoclax treatment.

³ For women of childbearing potential only. Must be done ≤7 days prior to registration, D1 of each induction cycle, Day 1 of each maintenance cycle, and end of maintenance. Test done ≤7 days prior to cycle1 day 1 can serve as cycle 1 day 1 test.

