4.1 Survival Follow-up

	Survival Follow-up Phase ¹							
	Every 90 days until subsequent treatment or PD ² After subsequent treatment or PD ² q. 180 days Death New Primar							
Survival Follow Up	X	X	X	X	At each occurrence			

¹ If a patient is still alive 5 years after registration and they have completed protocol therapy, no further follow-up is required.

⁸ Patients with known cardiac dysfunction are required to have EKGs and assessments of left ventricular ejection fraction at screening and as clinically indicated afterwards.

⁹ PET/CT in maintenance and post treatment every 6 months or per standard of care.

¹⁰ Baseline bone marrow biopsy and aspirate can be collected within 90 days of registration if negative. However, if bone marrow is positive after most recent therapy (even if greater than 90 days prior to registration), bone marrow biopsy and aspirate does not need to be repeated, but must be recorded as positive on the pre-treatment staging. Repeat Bone Marrow biopsy only in patients who are bone marrow positive at baseline and a CR at EOI to confirm EOI CR. Repeat Bone Marrow biopsy not needed in maintenance.

¹¹ Tissue specimen optional at the end of cycle 1 and optional at the time of progression. See Section 17.0 for additional details.

¹² Draw at baseline (drawn after registration but prior to cycle 1 treatment), day 1 of cycle 3, day 1 of cycle 7, day 1 of final maintenance cycle, and one year after completion of maintenance if patient is a CR. See Section 14.0 for further details.

¹³ Screen all patients for hepatitis B (HBV) infection before initiating treatment with Rituxan. For patients who show evidence of prior hepatitis infection, consult an expert in managing hepatitis B regarding monitoring and consideration for HBV antiviral therapy before and/or during Rituxan treatment (see Section 9.5).

¹⁴ If HIV testing is done \leq 180 days prior to registration it does not need to be repeated.

¹⁵ Patients will be required to keep a medication diary for venetoclax using the diary in Appendix V. Sites will be required to upload medication diary to RAVE at the end of each cycle.

¹⁶ Hematology and chemistry will be obtained prior to administering venetoclax (predose) and 8 and 24 hours after the first dose only. Laboratory samples should be sent and analyzed immediately.

¹⁷ MRD Testing to be completed at Mayo Clinic Rochester for patients who consent to optional collection.

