11.1 Response Considerations

Schedule of Evaluations: PET/CT scans are required at baseline for all patients. For the purposes of this study, patients should be reevaluated for disease progression at the end of induction therapy and every 6 months during maintenance or per standard of care. Definitions for clinical response for patients with lymphoma are from the recently revised Cheson's et al criteria published in 2014, derived from the original criteria published in 2007. (Cheson et al, 2014) (Cheson et al, 2007). Lymph node measurements should be taken from the CT portion of the PET/CT, or other dedicated CT scans where applicable. Measurement of lymphadenopathy for purposes of assessing for PR will be determined by adding the sum of the products of the maximal perpendicular diameters of measured lesions (SPD). The PPD of a single node is sufficient to evaluate for PD (see Table 11.2). Measurable extranodal disease should be assessed in a manner similar to that for nodal disease. For these recommendations, the spleen is considered nodal disease. Disease that is only assessable (eg, pleural effusions, bone lesions) will be recorded as present or absent only, unless, while an abnormality is still noted by imaging studies or physical examination, it is found to be histologically and pathologically negative.

Response is based on PET/CT based on the revised 2014 Lugano Classification. (Cheson et al, 2014).

Progressive disease is based on either PET-CT based or CT based response criteria. PET confirmation of progressive disease is per physician discretion.

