16.0 Statistical Considerations and Methodology

16.1 Overview:

This is a single arm Phase II study of combination of polatuzumab vedotin, venetoclax

and rituximab and hyaluronidase human in patients with relapsed or refractory mantle cell lymphoma (MCL). The relapsed/refractory MCL patient population will include both ibrutinib-naive and ibrutinib-pretreated patients. An early safety analysis will be conducted in patients with B cell NHL who have relapsed or progressed after at least one line of therapy prior to continuing accrual in this phase II study.

16.11 Primary Endpoint: The primary endpoint of this trial is the complete response rate at the end of induction by PET-CT scans according to Lugano 2014. A complete response will be considered synonymous with "success", unless specified otherwise. All patients meeting the eligibility criteria, who have signed a consent form and have begun treatment, will be evaluable for response, unless they are determined to be a major violation.

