16.32 Secondary Outcome Analysis

- 16.321 The overall response rate (ORR) at the end of induction will be estimated by the total number of patients who achieve a CR or PR by PET-CT scans according to Lugano 2014 divided by the total number of evaluable patients. All evaluable patients will be used for this analysis. Exact binomial 95% confidence intervals for the true overall response rate will be calculated. The ORR between ibrutinib-naive and ibrutinib-pretreated patients will be compared using Fisher's exact test.
- 16.322 The Best Response Rate to maintenance therapy will be evaluated. CR, PR and SD rates for patients who continue to maintenance will be estimated by number of patients who continue on maintenance therapy and achieve CR, PR or SD, respectively, at the end of maintenance divided by the total number of evaluable patients who continue to maintenance. Conversion rate from PR to CR will be evaluated by the number of patients achieving CR at EOM divided by the total number of patients who continue to maintenance in PR. Conversion rate from SD to PR or SD to CR will be evaluated by the number of patients achieving PR or CR, respectively at EOM divided by the total number of patients who continue to maintenance in SD.
- 16.323 Progression free survival (PFS) is defined as the time from registration to the earliest date of documentation of disease progression by CT or

- PET/CT or death due to any cause. The distribution of progression-free survival will be estimated using the method of Kaplan-Meier⁴. The PFS between ibrutinib-naive and ibrutinib-pretreated patients will be compared using log-rank test.
- 16.324 Overall survival (OS) is defined as the time from registration to death due to any cause. The distribution of OS will be estimated using method of Kaplan-Meier. The OS between ibrutinib-naive and ibrutinib-pretreated patients will be compared using log-rank test.
- 16.325 AEs: All eligible patients that have initiated treatment will be considered evaluable for assessing AE rate(s). The maximum grade for each type of AE from each patient will be used for analysis, and frequency tables will be reviewed to determine patterns. Additionally, the relationship of the AE(s) to the study treatment will be taken into consideration.
- 16.326 Correlative Analysis: Due to the small overall sample size, the results of these analyses will be considered exploratory and hypothesis- generating in nature.

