16.6 Results Reporting on ClinicalTrials.gov

At study activation, this study will have been registered within the "ClincialTrails.gov" website. The Primary and Secondary Endpoints along with other required information for this study will be reported on For purposes of timing of the Results Reporting, the initial estimated completion date for the Primary Endpoint of this study is 2.5 years after the study opens to accrual. The definition of "Primary Endpoint Completion Date" (PECD) for this study is at the time all patients registered have achieved a confirmed complete response during induction or have completed induction treatment without achieving a confirmed complete response.

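### Does the marrow biopsy in footnote 10, or the reference to a confirmed CR in 16.6, leave the primary complete response undefined?

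*Combined protocol and SAP*

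**What the plan says.** Section 16.11 names the primary endpoint as "the complete response rate at the end of induction by PET-CT scans according to Lugano 2014". Section 16.311 repeats it, adds that the response is taken "as determined by investigator on the basis of PET-CT scans according to Lugano 2014", and closes the definition: "A complete response is defined as an objective status of CR at the end of induction". The secondary response rate in 16.321 uses the same basis, counting "the total number of patients who achieve a CR or PR by PET-CT scans according to Lugano 2014". Section 11.1 bases response on PET/CT, and 1.53 does the same for EOI response.

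Two passages use other words. Footnote 10 to the test schedule reads: "Repeat Bone Marrow biopsy only in patients who are bone marrow positive at baseline and a CR at EOI to confirm EOI CR". Section 16.6 defines the primary endpoint completion date for the registry as the time when all registered patients "have achieved a confirmed complete response during induction or have completed induction treatment without achieving a confirmed complete response".

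On timing, footnote 1 to the test schedule states: "End of induction (EOI) is between 28-42 days after the last induction dose of rituximab and hyaluronidase human and polatuzumab vedotin". Section 11.1 says that "patients should be reevaluated for disease progression at the end of induction therapy and every 6 months during maintenance or per standard of care". The schedule shows no PET-CT in cycles 1 to 6.

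**The concern.** The decision rules are small counts: at least 4 CRs in 16 patients to continue, and at least 11 in 46 to call the regimen promising. Moving one patient between CR and PR can matter at either boundary.

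Footnote 10 asks for a biopsy to confirm the CR, but does not say what happens to the count if the biopsy is positive, missing or indeterminate. Nothing in Section 16 mentions the biopsy. Because the investigator determines CR, two sites could score the same patient differently.

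Section 16.6 raises a second difficulty. It leaves *confirmed* undefined and refers to a response during induction, when no response scan is planned. Read strictly, no patient can meet its first limb, and its second limb is met when induction treatment ends, before the scan that measures the endpoint.

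**Working it through.** **1. The stated design.** Inputs from 16.21 to 16.24: 16 patients at the interim, stop at 3 or fewer; 46 in total, promising at 11 or more. With true CR rate p,

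pass(p) = sum over x from 4 to 16 of P(Bin(16,p) = x) × P(Bin(30,p) ≥ 11 − x); stop(p) = P(Bin(16,p) ≤ 3).

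| p | pass(p) | stated | stop(p) | stated |
|---|---|---|---|---|
| 0.15 | 0.0486 | 0.049 | 0.7899 | 0.790 |
| 0.20 | 0.2124 | 0.212 | 0.5981 | 0.598 |
| 0.25 | 0.4672 | 0.467 | 0.4050 | 0.405 |
| 0.30 | 0.6995 | 0.700 | 0.2459 | 0.246 |
| 0.35 | 0.8506 | 0.851 | 0.1339 | 0.134 |

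The table reproduces. It holds for whatever is counted as a success, so the only question is what is counted.

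**2. What each passage does.**

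| Place | Role | Basis |
|---|---|---|
| 16.11, 16.311 | define success | PET-CT at EOI |
| 16.321 | scores ORR at EOI | PET-CT |
| 11.1, 1.53 | response basis | PET-CT |
| 11.2, PET-CT column, CR | marrow criterion | absence of FDG-avid disease |
| 11.2, CT column, CR | marrow criterion | morphology |
| Footnote 10 | orders a procedure | biopsy in patients already in CR at EOI |
| 16.6 | sets a registry date | undefined confirmation |

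A patient whose marrow is PET-negative but biopsy-positive meets the marrow row of the PET-CT column. Morphology is a criterion only in the CT column, which 16.311 does not use. Footnote 10 itself takes the EOI CR as already assigned when it selects whom to biopsy. The definition therefore gives one answer.

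**3. Size if the biopsy were allowed to overturn CRs.** The documents give no overturn share, so f is an assumption. If each PET-CT CR is overturned independently with probability f, confirmed CRs occur at rate p(1 − f) and can never outnumber PET-CT CRs. The chance that the two scorings give opposite final decisions is then pass(p) − pass(p(1 − f)); for the interim it is stop(p(1 − f)) − stop(p).

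| f | Expected overturned at p = 0.35 (46 × 0.35 × f) | Final, p = 0.35 | Final, p = 0.25 | Interim, p = 0.35 | Interim, p = 0.25 |
|---|---|---|---|---|---|
| 1% | 0.16 | 0.008 | 0.013 | 0.006 | 0.009 |
| 2% | 0.32 | 0.016 | 0.026 | 0.013 | 0.018 |
| 5% | 0.81 | 0.044 | 0.066 | 0.034 | 0.046 |
| 10% | 1.61 | 0.097 | 0.132 | 0.073 | 0.094 |

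If exactly one CR is overturned, placed at random among s CRs, the final decision reverses with probability P(s = 11, interim passed) + sum over s > 11 of P(s, interim = 4) × 4/s. This is 0.058 at 35% and 0.112 at 25%.

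**4. Timing under 16.6.** Five 21-day cycles put day 1 of cycle 6 at day 5 × 21 + 1 = 106, and its day 21 at day 126. EOI is day 106 + 28 = 134 to 106 + 42 = 148. The gap is 28 to 42 days from the last antibody dose, or 8 to 22 days from the end of cycle 6. At 2 to 3 patients per month (16.23), between 8 × 2/30.4 = 0.5 and 42 × 3/30.4 = 4.1 patients would lack an EOI scan on the strictest reading.

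The planned calendar covers this. Treatment starts at most 21 days after registration (6.44), so EOI comes at most 21 + 147 = 168 days after registration if no cycle is delayed. Sections 16.23 and 16.3 place results no earlier than 6 months (about 182 days) after the last patient is accrued, and 16.3 starts the analysis once patients are evaluable for the primary endpoint.

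**The case for a change.** The best argument for a change is that 16.311 leaves CR to the investigator, and the same protocol tells that investigator to obtain a biopsy in order to confirm it. A site could reasonably downgrade a PET-negative, biopsy-positive patient to PR. If all sites did so and 10% of PET-CT CRs were lost, power at a 35% PET-CT CR rate would fall from 0.851 to 0.754. A sentence settling the matter before the interim would be cheap.

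Part of this stands. Footnote 10 does not say what becomes of a positive or missing biopsy, and the wording of 16.6 does not fit the scan schedule. But the power loss arises only if sites depart from 16.311 and 11.2. It reaches only patients who were marrow-positive at baseline and reach PET-CT CR. It leaves ORR and entry to maintenance unchanged, because CR and PR are treated alike there (7.2). Section 18.5 calls for imaging and pathology reports at restaging, so a status scored on histology can be seen and checked against the PET-CT definition.

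Ruling that the biopsy never counts would also be more than a tidy-up. It would empty footnote 10 of its stated purpose, and that choice belongs to the sponsor.

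**Conclusion.** No change to the plan is needed. The primary endpoint has one operative definition: investigator-read PET-CT CR at EOI, with the marrow judged by FDG avidity. An analyst following Section 16 and 11.2 reaches the same counts, error rates (0.049 and 0.851) and decision whether or not the other two passages are reworded. Footnote 10 leaves a gap that the definition fills. Section 16.6 is a loosely worded reporting date that does not trigger the analysis.

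The discordance probabilities, about 1% to 10% at a 35% CR rate and 1% to 13% at 25%, rest on assumed overturn shares of 1% to 10%, independent between patients, under a reading Section 16 does not adopt. The calendar argument assumes no cycle delay and leaves about 182 − 168 = 14 days in hand. With longer delays, the evaluability condition in 16.3 still governs when the analysis starts.

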16.32 Secondary Outcome Analysis

- 16.321 The overall response rate (ORR) at the end of induction will be estimated by the total number of patients who achieve a CR or PR by PET-CT scans according to Lugano 2014 divided by the total number of evaluable patients. All evaluable patients will be used for this analysis. Exact binomial 95% confidence intervals for the true overall response rate will be calculated. The ORR between ibrutinib-naive and ibrutinib-pretreated patients will be compared using Fisher's exact test.
- 16.322 The Best Response Rate to maintenance therapy will be evaluated. CR, PR and SD rates for patients who continue to maintenance will be estimated by number of patients who continue on maintenance therapy and achieve CR, PR or SD, respectively, at the end of maintenance divided by the total number of evaluable patients who continue to maintenance. Conversion rate from PR to CR will be evaluated by the number of patients achieving CR at EOM divided by the total number of patients who continue to maintenance in PR. Conversion rate from SD to PR or SD to CR will be evaluated by the number of patients achieving PR or CR, respectively at EOM divided by the total number of patients who continue to maintenance in SD.
- 16.323 Progression free survival (PFS) is defined as the time from registration to the earliest date of documentation of disease progression by CT or

- PET/CT or death due to any cause. The distribution of progression-free survival will be estimated using the method of Kaplan-Meier⁴. The PFS between ibrutinib-naive and ibrutinib-pretreated patients will be compared using log-rank test.
- 16.324 Overall survival (OS) is defined as the time from registration to death due to any cause. The distribution of OS will be estimated using method of Kaplan-Meier. The OS between ibrutinib-naive and ibrutinib-pretreated patients will be compared using log-rank test.
- 16.325 AEs: All eligible patients that have initiated treatment will be considered evaluable for assessing AE rate(s). The maximum grade for each type of AE from each patient will be used for analysis, and frequency tables will be reviewed to determine patterns. Additionally, the relationship of the AE(s) to the study treatment will be taken into consideration.
- 16.326 Correlative Analysis: Due to the small overall sample size, the results of these analyses will be considered exploratory and hypothesis- generating in nature.
- 16.327 MRD Analysis: MRD will be assessed on whole blood using the Roche panel at pre-treatment, end of induction, and end of maintenance.

 MRD status for both responders and non-responders at each time point will be reported descriptively and explored for correlation with clinical factors and patient outcomes such as PFS and OS. Changes in MRD status from baseline to end of induction and end of maintenance will also be summarized.
- 16.328 T cell and cytokine subsets: Systemic immune profiles and T cell activation will be investigated using multi-parameter flow cytometry, and cytokine analysis in the peripheral blood of patients at the following timepoints: a) pre-treatment, b) early in treatment (cycle 3), c) end of induction (cycle 7), d) end of maintenance year 1 (cycle 18), f) end of maintenance year 2. The results from T cell and Cytokine subsets analysis will be reported descriptively by median, min, max, and interquartile range.
- 16.329 High risk cytogenetic alterations and other risk stratification scores will be summarized using frequency and percentages.

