2.2 Secondary Endpoints

- 2.21 To evaluate the EOI overall response rate (ORR) for the combination of RSc+Pola+Ven in relapsed/refractory MCL.
- 2.22 To evaluate the best response (CR, PR) in patients who continue on to maintenance therapy and evaluate the improvement in the depth of response.
- 2.23 To evaluate the progression free survival (PFS) and overall survival (OS) for the combination of RSc+Pola+Ven in relapsed/refractory MCL.
- 2.24 To compare the ORR, CR, PFS, and OS in ibrutinib refractory compared to ibrutinib naïve patients.

2.25 To evaluate regimen-related toxicity for patients treated with RSc+Pola+Ven.

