3.0 Patient Eligibility

For patients in the safety run in, prior to discussing protocol entry with the patient, call the ACCRU Registration Office (or email at a place on the protocol is open to the patient.

NOTE: Waivers to eligibility criteria are not allowed per ACCRU policy

- **3.1** Registration Inclusion Criteria
 - 3.11 Age \geq 18 years.
 - 3.12 Pathologically confirmed relapsed or primary refractory mantle cell lymphoma with concurrent or prior tissue sample IHC positive for cycle in D1 or that is positive for FISH or cytogenetics for t(11;14).

NOTE: Safety Portion only: MCL or indolent B cell NHL (FL (grades I-IIIa) MZL), or SLL stratified as low risk for TLS, relapsed or progressed after at least two lines of therapy, or one line of a BTK inhibitor containing therapy, or Autologous Stem Cell Transplant (AutoSCT). No limit to prior lines of therapy.

NOTE: Expansion Portion only: MCL relapsed or progressed after at least two lines of therapy, or one line of a BTK inhibitor containing therapy, or Autologous Stem Cell Transplant (AutoSCT). No limit to number of prior therapies. May have received prior BTK inhibitor therapy.

- 3.13 Measurable disease as defined with at least one lesion measuring \geq 1 x 1.5cm by PET/CT using Lugano criteria.
- 3.14 ECOG Performance Status of 0, 1, or 2. (Form is available on the ACCRU web

site under Study Resources -> Forms)

- 3.15 The following laboratory values obtained \leq 14 days prior to registration.
 - Absolute neutrophil count (ANC) ≥1000/mm³
 - Platelet count \geq 75,000/mm³
 - Hemoglobin ≥9.0 g/dL
 - International normalized ratio ≤ 1.5 x ULN for patients not receiving therapeutic anticoagulation
 - Partial thromboplastin time (PTT) or activated PTT (aPTT) $\leq 1.5 \text{ x ULN}$
 - Adequate liver function, as indicated by: AST and ALT $\leq 2.5 \times \text{ULN}$
 - Total bilirubin $< 1.5 \times ULN$ (or $\le 3 \times ULN$ for patients with documented Gilbert syndrome)
 - Adequate renal function as indicated by: calculated Cr clearance ≥45 ml/min using the modified Cockcroft-Gault formula (eCCr; with the use of ideal body mass [IBM] instead of mass):

eCCr =
$$\frac{(140 - \text{Age}) \times \text{IBM (kg)} \times [0.85 \text{ if female}]}{72 \text{ x serum creatinine (mg/dL)}}$$

Or, if serum creatinine is in µmol/L:

eCCr =
$$\frac{(140 - \text{Age}) \times \text{IBM (kg)} \times [1.23 \text{ if male, } 1.04 \text{ if female}]}{\text{serum creatinine (}\mu\text{mol/L)}}$$

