16.2 Statistical Design

- 16.21 Decision Rule: The largest success proportion where the proposed treatment regimen would be considered ineffective in this population is 15%, and the smallest success proportion that would warrant subsequent studies with the proposed regimen in this patient population is 35%. The following one-stage design with an interim analysis is based on a two-stage Simon optimum design² and requires 46 evaluable patients to test the null hypothesis that the true success proportion in this patient population is at most 15%.
 - 16.211 Interim Analysis: Enter 16 evaluable patients into the study. If 3 or fewer successes are observed in the first 16 evaluable patients, we will consider this regimen ineffective in this patient population and terminate the study. Otherwise, if the number of successes is at least 4, we will continue accrual.
 - 16.212 Final Decision Rule: Enter an additional 30 evaluable patients into the study. If 10 or fewer successes are observed in the first 46 evaluable patients, we will consider this regimen ineffective in this patient population and terminate the study. Otherwise, if the number of success is at least 11, this will be considered evidence of promising activity and the treatment may be recommended for further testing in subsequent studies in this population.
 - 16.213 Over Accrual: If more than the target number of patients are accrued, the additional patients will not be used to evaluate the stopping rule or used in any decision-making process. Analysis involving over accrued patients is discussed in section 16.313.

NOTE: We will not suspend accrual at the interim analysis to allow the first 16 patients to become evaluable, unless undue toxicity is observed. Given the limited overall sample size and the inclusion of an AE stopping rule, we feel it is ethical to not halt accrual for the interim analysis. However, if accrual is extremely rapid, we may temporarily suspend accrual in order to obtain safety data on these patients before reopening accrual to further patients.

- 16.214 Dose de-escalation in safety analysis: A safety analysis will be performed in the first 6 evaluable patients per Section 16.4. In the case of unacceptable toxicity, the dose will be de-escalated. If this occurs, the first 6 patients will be evaluated separately and will not be included in any decision-making criteria.

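### The ORR analysis set in Section 16.321 is not limited to MCL at the final dose level, which conflicts with goal 2.21 and with the separation stated in 16.311

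*Combined protocol and SAP*

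**What the plan says.** Section 16.321 divides the patients in CR or PR at the end of induction by the number of evaluable patients, and adds: "All evaluable patients will be used for this analysis". It also compares ORR between ibrutinib-naive and ibrutinib-pretreated patients by Fisher's exact test.

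Evaluability is defined in 16.311 (and in near-identical terms in 16.11): "All patients meeting the eligibility criteria who have signed a consent form and have begun treatment will be evaluable for response", except for major violations. Section 3.12 sets eligibility with a note: "Safety Portion only: MCL or indolent B cell NHL". The indolent types listed are FL, MZL and SLL.

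Goal 2.21 is: "To evaluate the EOI overall response rate (ORR) for the combination of RSc+Pola+Ven in relapsed/refractory MCL".

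The passages that narrow the population are in other sections:
- 16.311, on the primary endpoint: "Only MCL patients treated at the final dose level will be included when evaluating the decision rules in Sections 16.211 and 16.212". The next sentence reads: "Patients without MCL and patients treated at other dose levels will be summarized separately".
- 16.214, on de-escalation: "If this occurs, the first 6 patients will be evaluated separately and will not be included in any decision-making criteria".
- 16.22, on sample size, carries run-in patients into phase II only if they have MCL and were treated at the final dose level.

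Section 16.32 neither repeats nor refers to any of these. Section 16.322 (response in maintenance) uses evaluable patients who continue to maintenance. Sections 16.323 and 16.324 (PFS and OS) name no analysis set.

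**The concern.** A statistician programming ORR will start from 16.321, look up evaluable, and find no condition on histology or dose. The resulting set is wider than the population in goal 2.21. It mixes lymphoma types and, after a de-escalation, dose levels. The same set feeds the Fisher test, so the comparison by ibrutinib history could partly reflect histology.

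At stake are the interpretation of the main secondary response estimate and the risk that the analysis set is chosen once the data are known. With so few patients, a handful from outside the target population can visibly move a proportion.

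**Working it through.** **1. The plan's own totals (16.22).** 46 evaluable MCL patients + 6 if the dose is de-escalated + 5 allowance = 57. Adding 6 if no safety-portion patient has MCL gives 57 + 6 = 63. Both stated totals reproduce, and 63 is also the total in the accrual table of 16.73. Non-MCL run-in patients are thus a planned scenario.

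**2. Does evaluable exclude them?** The definition requires eligibility, consent, start of treatment and no major violation. A run-in patient with FL, MZL or SLL can meet all four, and so can an MCL patient at an abandoned dose. Sections 16.214 and 16.22 themselves call run-in patients evaluable.

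**3. How many could be outside the target population?**
- No de-escalation, none of the 6 run-in patients with MCL: 46 + 6 = 52, and 6/52 = 11.5%.
- De-escalation, first 6 at the abandoned dose, all 6 replacements without MCL: 46 + 6 + 6 = 58 (equal to 63 − 5), and 12/58 = 20.7%.

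These are upper limits, before any over-accrual of MCL patients.

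**4. How far could ORR move?** Let x of 46 target patients respond, and y of k additional patients. Then

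shift = (x + y)/(46 + k) − x/46.

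The documents give no expected ORR for the regimen, so x is an assumption, with x/46 from about 50% to 80%. The extremes are y = 0 and y = k.

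| k | Largest fall | Largest rise |
|---|---|---|
| 6 | 37/46 = 80.4% to 37/52 = 71.2%: −9.3 points | 23/46 = 50.0% to 29/52 = 55.8%: +5.8 points |
| 12 | 37/46 = 80.4% to 37/58 = 63.8%: −16.6 points | 23/46 = 50.0% to 35/58 = 60.3%: +10.3 points |

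A middle case is x = 32, or 69.6% (exact 95% interval 54.2% to 82.3%). Six additional patients give 61.5% if none respond, 67.3% if three do, and 73.1% if all do. Twelve give 55.2%, 65.5% (six respond) and 75.9%. Except at the extremes, the shift is small beside the interval.

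The documents do not say how many run-in patients will be ibrutinib-naive, so no figure is given for the naive versus pretreated comparison.

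**5. Is the CR design touched?** P(stop early) = P(X₁ ≤ 3 | n = 16). P(positive) = Σ over x = 4 to 16 of P(X₁ = x) × P(X₂ ≥ 11 − x | n = 30).

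| True CR rate | P(positive), exact | Plan | P(stop early), exact | Plan |
|---|---|---|---|---|
| 0.15 | 0.0486 | 0.049 | 0.7899 | 0.790 |
| 0.35 | 0.8506 | 0.851 | 0.1339 | 0.134 |

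The table in 16.24 reproduces. Section 16.311 already limits the decision rules to MCL at the final dose level, so these figures stand.

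**The case against.** The strongest reply is that the document, read as a whole, already answers the question. The 16.311 sentence on separate summaries carries no limit to the decision rules. Section 16.214 sets aside the first 6 patients after de-escalation, and 16.22 admits only final-dose MCL patients to phase II. Goals 2.21 and 2.23 name MCL. The unqualified term evaluable is also used in 16.211, 16.212 and 16.312, where MCL at the final dose is plainly meant. The word all in 16.321 may mean only that ORR is not capped at the first 46 patients, in line with the over-accrual rule in 16.313. Section 5.3 plans at least 25 ibrutinib-naive and at most 26 pretreated patients at the chosen dose level; 25 + 26 = 51 = 46 + 5, which suggests that the comparison was meant for the phase II population.

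Much of this stands as evidence of intent, and a reader should not infer that the plan deliberately pools lymphomas or doses. It does not remove the conflict. The 16.311 sentence sits under the primary endpoint, directly after a restriction tied to the CR rules. Section 16.214 applies only after de-escalation and does not reach non-MCL patients at a dose that passes. Section 16.22 concerns sample size. The only section that defines the ORR set states it without restriction and points to none of these.

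**Conclusion.** The point holds as a conflict over the ORR analysis set. Section 16.321, taken literally, gives a population different from the one in goal 2.21 and from the intent shown in 16.311, 16.214 and 16.22. At most 6 of 52 (11.5%) or 12 of 58 (20.7%) evaluable patients would be affected. The first figure assumes no MCL patient in the run-in; the second also assumes de-escalation after a full first cohort and no MCL patient among the replacements.

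Three stronger readings are tempting and are not supported:
- That ORR would be inflated. The direction is unknown. The only loosely relevant figures, for single-agent polatuzumab vedotin in 1.232, are 7 of 16 (44%) in indolent lymphoma at 2.4 mg/kg and 6 of 7 in MCL. They point the other way if anything, and are too few and too remote from the triplet to settle it.
- That PFS and OS will be pooled. Sections 16.323 and 16.324 are silent, and silence is not an instruction to pool. They need the restriction stated; they do not contradict it.
- That the trial's conclusion is at risk. ORR carries no decision rule or power, and the CR rules, type I error and power are unchanged.

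The plan should be corrected before analysis, but this is a matter of clarity in a secondary endpoint.

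**What to change.** In 16.321, replace the sentence on the analysis set with one saying that ORR uses every evaluable patient who has MCL and was treated at the final dose level. State once in 16.32 that the same set applies to 16.322, 16.323 and 16.324 and to every ibrutinib-naive versus pretreated comparison. Add that patients without MCL and patients at other dose levels are summarized separately, as 16.311 provides.

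The cost is a few words in the analysis plan and a slightly smaller ORR denominator: 46 instead of up to 52 or 58, before over-accrual. No sample size, data collection or decision rule changes.
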